#### **7.7. Follow-up of subjects withdrawn from treatment**

Any withdrawn patient will be followed up to obtain at least safety information (i.e. collection of adverse events) only when this patient received at least one vaccination. In addition, every effort should be made to perform as much as possible the efficacy assessments.

## **7.8. Premature termination of the study**

Both the investigator and the sponsor reserve the right to terminate the study for reasons of safety, important ethical issues or severe non-compliance. Reason for premature termination of the study can be the occurrence of SAE or suspected unsuspected serious adverse reactions (SUSAR). In (prematurely) terminating the study, the sponsor and the investigator will ensure that adequate consideration is given to the protection of the best interests of the patients. This study may also be ended or suspended by competent authorities or by the Central Committee on Research involving Human Subjects (CCMO).

## **7.9. Description of assessments**

### **7.9.1. Medical history**

Specific information will be recorded on the case report form (CRF) relating to any prior or existing medical conditions/surgical procedures involving the following: infectious diseases, oncologic diseases, allergic, metabolic/endocrine/nutritional, hematopoietic, musculoskeletal, dermatologic, head/ears/eyes/nose/throat (HEENT), breasts, respiratory, cardiovascular, gastrointestinal/hepatic, genitourinary/renal, neurologic, and psychiatric/psychosocial.

### **7.9.2. Standard physical examinations, and vital signs**

The standard physical examination will include the following observations/measurements: general appearance, skin, HEENT, lymph nodes, heart, lungs, breasts, abdomen, extremities/joints, neurological, mental status, and vital signs, including systolic and diastolic blood pressures (mmHg), heart rate (beats/minute), respiratory rate (breaths/minute), and temperature (degrees of Celsius).

If a clinically relevant worsening in a baseline standard physical examination parameter is observed upon vaccination, the change will be documented as an AE on the AE page of the CRF. Clinical relevance is defined as any variation in physical findings, which has medical consequences that result in an alteration in medical care. The investigator will continue to monitor the patient until the parameter returns to baseline level or until the investigator determines that follow-up is no longer medically necessary.

### **7.9.3. Blood collection**

For hematology and biochemistry: 12.5 ml of venous blood (1 x 4 ml + 1 x 8.5 ml) will be obtained during the screening visit, before second and third vaccination (week 3 and 6, respectively) and at follow up (week 9 and week 26). For immunological assessment: 81 ml (9 x 9 ml) of venous blood will be obtained before vaccination (week 0), before third vaccination (week 6), at first follow up (week 9) and at third follow up (week 26). A total volume of 386.5 ml blood will be drawn during this trial.

#### 7.9.4. Serum chemistry and hematology tests

Serum chemistry profile: albumin, alkaline phosphatase (AP), alanine transaminase (ALT), aspartate transaminase (AST), urea, calcium, chloride, creatinine, gamma glutamyl transferase (γGT), gamma globulin, phosphate, potassium, sodium, total bilirubin, total protein.

Hematology: INR, aPTT, white blood cell (WBC) count with differential, hemoglobin, hematocrit, platelet count, red blood cell (RBC) count. For these two analyses methods a total of 15 mL blood will be collected by venous puncture.

A serum pregnancy test will be performed in females of child-bearing potential only at the screening visit. These patients will also have a urine pregnancy test performed prior to each vaccination.

The Investigator must score all abnormal laboratory values as either clinically relevant, or not clinically relevant. Clinical relevance is defined as any variation in laboratory parameters that has medical consequences that result in an alteration in the patient's medical care. If clinically relevant worsening from baseline levels is noted, the changes will be documented on the AE page of the CRF. The Investigator will also assess the relationship of all clinically relevant abnormal values to study medication as being none, remote, possible, probable, or definite. The Investigator will continue to monitor the patient with additional laboratory assessments until (1) values have reached normal range and/or baseline levels, or, (2) in the judgment of the investigator, the abnormal values are not related to the administration of study medication or other protocol-specific procedures.

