### 3. STUDY DESIGN

This single center phase I trial will determine the biological activity of Hespsecta within the proposed dose range that induces HPV16 E6-specific immunity. In addition, this study will evaluate toxicity of vaccination with Hespsecta. This translational dose escalation phase I trial will be performed in 4 dose groups (1, 5, 20 or 50 µg/peptide), each group consisting of 6 patients (see paragraph 4.4). Patients will receive i.d. injections three times with a fixed dose of Hespsecta at an interval of every three weeks. Patients diagnosed with HPV16+ (pre-)malignant lesions will be informed of this study. They will be included at least one month after the last standard treatment (for details see paragraph 4). Patients will be recruited at the LUMC, including referrals from other hospitals. The HPV type will be determined in tumor tissue by the department of pathology using standard operating procedures (SOPs). After obtaining informed consent, patients will be screened for eligibility in the study. Safety will be assessed during the study by collecting all AE according to the CTCAE version 4 (see paragraph 7.1). Venous blood samples at different time points will be obtained for immunomonitoring and clinical parameters for safety establishment. Immunological responses will be determined in isolated PBMCs of all vaccinated patients at the different time points (for details see paragraph 7). The decision to start enrolment at the next dose level will be made by assessing the safety after 4 out of 6 patients at the previous dose level have completed the first follow up visit after the third vaccination. The Principal Investigator (PI) will employ listings of individual patient data related to baseline characteristics, safety, and study medication administration for the patients necessary to assess per above before decision to start enrolment at the next dose level. The PI will assess information per above for relevant patients, summarize findings, and give a recommendation whether or not he endorses the start of enrolment at the next dose level. The summary and recommendation from the PI, including all necessary individual patient background material, should be reviewed and commented on by the Independent Data Monitoring Committee (IDMC) members. After having received the opinion of the IDMC, the PI can issue a written approval (or disapproval) regarding the start of enrolment at the next dose level. If in two or more patients CTCAE grade 3 or 4 treatment related toxicity occurs the dose escalation phase will be discontinued. If in the lowest dose group two patients experience CTCAE grade 3 or 4 treatment related toxicity, there is no safe dose and the study will be discontinued.

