### 7.2. Secondary study parameters/endpoints

Safety will be determined by the incidence rate at each dose level based on the following safety parameters: adverse events (AE) and serious (SAE), changes in hematology and chemistry values, including those associated with hepatic and renal function, and assessment of physical examinations, vital signs and performance status using NCI-CTCAE version 4.0

[figure not shown]
([http://ctep.cancer.gov/protocolDevelopment/electronic\\_applications/ctc.htm#ctc\\_40](http://ctep.cancer.gov/protocolDevelopment/electronic_applications/ctc.htm#ctc_40)).

NL48274.000.14

Phase I Study: Hespsecta vaccination in HPV+ lesions

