### 9.2. Safety

The safety analysis will be performed on all subjects receiving at least one dose of study medication. Adverse events (AEs) will be tabulated by system organ class using the MedDRA dictionary, and by severity according to CTCAE criteria, version 4.0.

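### Sections 7.9.2 and 7.9.4 tie AE entry, and for laboratory values the relatedness rating, to a change in care rather than CTCAE grade, so the two-patient stopping count can miss an observed grade 3-4 value

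*Protocol*

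**What the plan says.** Section 7.9.4 has the investigator score each abnormal laboratory value as clinically relevant or not, with this test: "Clinical relevance is defined as any variation in laboratory parameters that has medical consequences that result in an alteration" in the patient's care. Two steps depend on the score:

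- AE entry: "If clinically relevant worsening from baseline levels is noted, the changes will be documented on the AE page of the CRF".
- Relatedness: "The Investigator will also assess the relationship of all clinically relevant abnormal values to study medication", on a five-level scale from none to definite.

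Section 7.9.2 uses the same test for AE entry of examination findings, vital signs included: "Clinical relevance is defined as any variation in physical findings, which has medical consequences that result in an alteration in medical care".

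Other sections work on a different basis:

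- Section 2 sets the secondary objective as safety through collection of all AEs under CTCAE v4.0.
- Section 8.2.1 counts as an AE any unwanted occurrence in a participant, related or not. It does not ask whether care changed.
- Section 7.2 lists, beside AEs and SAEs, "changes in hematology and chemistry values, including those associated with hepatic and renal function", and assesses the safety parameters by dose level under CTCAE v4.0.
- Section 3 gives the numerical rule: "If in two or more patients CTCAE grade 3 or 4 treatment related toxicity occurs the dose escalation phase will be discontinued".
- Section 9.2 names one safety analysis: "Adverse events (AEs) will be tabulated by system organ class using the MedDRA dictionary, and by severity according to CTCAE criteria".

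**The concern.** CTCAE grade and change in care are different criteria. A liver-enzyme or blood-count change can reach grade 3 without symptoms and be watched until it settles. Section 7.9.4 does not require an AE entry or a relatedness rating for such a value, yet the Section 3 rule can count a patient only if the toxicity is both grade 3 or 4 and judged related. The rule therefore depends on a judgement that the data-collection section does not ask for.

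The error runs in one direction, toward under-counting. With six patients per dose in a first-in-man trial, one uncounted patient can decide whether the rule is met. A later analysis plan cannot repair this, because a rating that was never collected cannot be tabulated.

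**Working it through.** The protocol states no operating characteristics for the stopping rule, so there is no figure to reproduce. The check has two parts.

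**1. Follow one value through the text.** Take a post-vaccination laboratory value that worsens from baseline to grade 3, causes no change in care and later returns to baseline.

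| Place | Criterion applied | Result for this value |
|---|---|---|
| 7.9.4, AE page | Care altered | Entry not required |
| 7.9.4, relatedness | Care altered | Rating not required |
| 8.2.1, AE definition | Any unwanted occurrence | Would be an AE |
| 7.2, laboratory parameter | CTCAE v4.0, by dose level | Included |
| 9.2, AE tabulation | AEs by severity | Can be missing |
| Appendix 2 (IDMC charter, 14.2.2), listings before escalation | Individual hematology and biochemistry data | Visible |
| Section 3, two-patient rule | Grade 3-4 and related | Can be missing, because no rating is required |

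Sections 7.9.4 and 8.2.1 disagree on whether this is an AE, and 7.9.4 does not secure the relatedness input that Section 3 needs.

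**2. What the missing rating could do to the count.**

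Inputs from the protocol:
- threshold of 2 patients (Section 3);
- cohort of n = 6 (Section 4.4);
- escalation decision once 4 of the 6 have completed the first follow-up visit, so n = 4 (Section 3).

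Assumptions not in the protocol:
- p, the true per-patient rate of related grade 3-4 toxicity;
- c, the share of it that is rated;
- independent patients, with the rule applied within one cohort.

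With q = p × c,

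P(at least 2 of n) = 1 − (1 − q)^n − n·q·(1 − q)^(n−1).

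Worked cases:
- n = 6, p = 0.20, all rated (q = 0.20): 1 − 0.2621 − 0.3932 = 0.345.
- n = 6, p = 0.20, half rated (q = 0.10): 1 − 0.5314 − 0.3543 = 0.114.
- n = 4, p = 0.33, all rated (q = 0.33): 1 − 0.2015 − 0.3970 = 0.401.
- n = 4, p = 0.33, half rated (q = 0.165): 1 − 0.4861 − 0.3842 = 0.130.

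Range over the rated share:

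| n | p | c = 1 | c = 0.75 | c = 0.5 | c = 0.25 |
|---|---|---|---|---|---|
| 6 | 0.10 | 0.114 | 0.069 | 0.033 | 0.009 |
| 6 | 0.20 | 0.345 | 0.224 | 0.114 | 0.033 |
| 6 | 0.33 | 0.642 | 0.460 | 0.259 | 0.082 |
| 4 | 0.20 | 0.181 | 0.110 | 0.052 | 0.014 |
| 4 | 0.33 | 0.401 | 0.258 | 0.130 | 0.036 |

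The loss depends on c and disappears as c approaches 1.

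**The case against.** A reader might infer that silent grade 3-4 laboratory toxicity escapes both the safety endpoint and the escalation decision. The documents do not support that. Section 7.2 keeps hematology and chemistry changes as a safety parameter in their own right, so such a value remains in the endpoint. Before each dose step the IDMC charter supplies individual hematology and biochemistry listings, named separately from adverse events, so a member can see the value and object. Both points stand. They limit the finding to the AE tabulation and the formal count. IDMC review is a discretionary safeguard, though: the charter sets no laboratory threshold, and the listings would carry no required relatedness rating for these values.

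Three further arguments have some force:

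- **Section 7.9.4 does not forbid entering or rating other values, and Section 3 counts toxicity rather than AE entries.** True, so a value that is not clinically relevant is not barred from the count. But nothing requires the judgement that would put it there.
- **Section 7.9.4 also calls for extra laboratory checks until values recover or the investigator judges them unrelated.** The second ending is a relatedness judgement, and extra checks might be read as altered care. But monitoring can also end on recovery alone, with no such judgement, and the protocol does not say whether added tests count as altered care. Two investigators could classify the same value differently.
- **The assumed rates may be far too high.** Sections 1.7 and 10.3 report no toxicity in rabbits and, for the earlier vaccine, events generally no worse than grade 2. This is fair, and it is why the figures serve only as illustration.

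**Conclusion.** The concern holds in a limited form. The care-based test in 7.9.4, and in 7.9.2 for AE entry, conflicts with the AE definition in 8.2.1 and with the collection of all AEs in Section 2. It also fails to secure the relatedness judgement that the Section 3 rule uses. A grade 3-4 value that is only observed can therefore be absent from the AE table by severity and from the two-patient count, while remaining in the 7.2 laboratory parameter and in the IDMC listings.

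The protocol does not allow the size to be estimated. If half of related grade 3-4 events went unrated, the chance of meeting the count would fall by about two thirds in the worked cases (0.345 to 0.114, and 0.401 to 0.130). These figures rest wholly on assumed rates and an assumed unrated share, and they give no weight to IDMC review. The absence of a laboratory summary from Section 9.2 is not part of this finding, since a statistical analysis plan may contain one.

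**What to change.** Reconcile 7.9.2 and 7.9.4 with 7.2, 8.2.1 and Section 3. State in both assessment sections that every post-vaccination worsening from baseline to CTCAE grade 3 or higher, in a laboratory value or an examination finding, is entered on the AE page and rated for relatedness whether or not care changed. If the care-based test is kept for lower grades, say so in 8.2.1 so that the AE definition and the recording rule agree.

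This changes what is recorded. It does not change treatment or the stopping threshold. The cost is about two sentences and a CRF instruction. The downside is a few more AE entries and a less favourable AE table.

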#### 7.9.5. Immunological assessments

##### 7.9.5.1. HPV16 E6 and E7 peptide-specific proliferation assay

HPV16 E6 and E7 peptide-specific proliferation is determined using a short-term (6-day) assay. This assay has been published and found to be related to clinical outcome [10,18,32,53,54]. The average and standard deviation of the 8 medium only control wells are calculated and the cut-off is defined as this average plus 3xSD. The stimulation index (SI) is calculated as the average of 8 experimental wells divided by the average of the 8 medium control wells. A positive proliferative response is predefined as a SI of at least 3 and the counts of at least 6 out of the 8-wells must be equal or above the cut-off value [7].

##### 7.9.5.2. HPV16 E6 and E7 peptide-specific cytokine bead array

Supernatants from the peptide-specific proliferation assay are used to perform a cytokine bead array and measure cytokine production (IFN $\gamma$ , TNF $\alpha$ , IL-4, IL-5, IL-10, and IL-2). Positive antigen-specific cytokine production (in pg/ml) is defined as a cytokine concentration above the detection limit and >2x the concentration of the medium control. A vaccine-induced response is defined as a value (SI or cytokine level) which is at least 3-fold higher than the pre-vaccination response [7].

NL48274.000.14

Phase I Study: Hespecta vaccination in HPV+ lesions

#### 7.9.5.3. HPV16 E6 and E7 peptide-specific IFN $\gamma$ -ELISPOT for CD4+ T-cells

The 4-day IFN $\gamma$ -ELISPOT for the detection of HPV16 E6 and E7 peptide-specific CD4+ T cells is our standard and validated assay. Spots are counted with a fully automated computer-assisted-video-imaging analysis system (BioSys 5000). Specific spots are calculated by subtracting the mean number of spots in quadruplicate wells + 2xSD of the medium only control from the mean number of spots in experimental wells. Antigen-specific T-cell frequencies are considered to be increased compared to non-responders when specific T-cell frequencies are  $\geq 1/10,000$ . T-cell frequencies are considered to be boosted by the vaccine when they were at least 3-fold higher than those prior to vaccination [10,55,56,57].

#### 7.9.5.4. Ex-vivo HPV16 E6 and E7 peptide-specific responses

We have developed and validated a multiparameter flow cytometry assay. In this assay the HPV16-specific cytokines IFN $\gamma$  TNF $\alpha$ , and/or IL-2 producing CD4+ and/or CD8+ T cells can be simultaneously enumerated in combination with the activation markers CD154 and/or CD137. For this long overlapping HPV16 E6 and E7 peptides will be used to be able to detect both CD4 and CD8 T-cell responses in a HLA-independent setting as these long peptides harbor all potential CD4 and CD8 epitopes for every individual patient. Moreover, due to increased sensitivity in comparison to commonly applied intracellular cytokine staining (ICS) also low frequency antigen-specific T-cell responses can be detected directly ex vivo by using freshly isolated or cryopreserved PBMCs [58]. A positive response is defined as a frequency of activation marker expressing or cytokine producing T cells in the peptide stimulated condition which is twice above the medium only control. A vaccine-induced response is indicated by a 3-fold increase in frequency of antigen-specific T-cells (activation markers and/or cytokine production) compared to baseline values.

NL48274.000.14

Phase I Study: Hespecta vaccination in HPV+ lesions

## 8. SAFETY REPORTING

### 8.1. Section 10 WMO event

In accordance to section 10, subsection 1, of the WMO, the investigator will inform the subjects and the reviewing CCMO if anything occurs, on the basis of which it appears that the disadvantages of participation may be significantly greater than was foreseen in the research proposal. The study will be suspended pending further review by the CCMO, except insofar as suspension would jeopardize the subjects' health. The investigator will take care that all subjects are kept informed.

### 8.2. AEs, SAEs and SUSARs

#### 8.2.1. Adverse events (AEs)

AEs are defined as any undesirable experience occurring to a subject during the study, whether or not considered related to the investigational product. All AEs reported spontaneously by the subject or observed by the investigator or his staff will be recorded.

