**Nature and extent of the burden and risks associated with participation, benefit and group relatedness:** Patients will visit the clinic during the trial six or even additional times (screening visit, three vaccination visits, and three follow up visits (if no abnormalities are found during the first follow up visit, the second follow visit may take place by telephone,). These follow up visits are combined with regular treatment follow up visits. Potential risks with the current trial are mainly linked to the toxicity related to the treatment compounds utilized in Hespecta. Although the rabbit toxicity testing of Hespecta (see IMPD brochure) did not show any severe side effects, it is expected from previous results with HPV16-SLP, that the most important AEs of Hespecta may consist of fever, chills, nausea, malaise, fatigue and local reactions at the vaccination site including pain, redness, swelling and itching. Generally the AEs after vaccination with HPV16-SLP did not exceed grade 2 according to the CTCAE criteria. Almost all patients, vaccinated with HPV16-SLP formulated in Montanide ISA51 experienced local injection site reactions (grade 2). After vaccination, ulceration/abscess formation occasionally occurred, estimated to be in between 1 and 5% of vaccinations, due to the use of this Montanide as adjuvant. The current vaccine is administered without Montanide, and therefore, it is expected that these local reaction will be less severe. Allergic reactions have occurred in a few patients after HPV16-SLP vaccinations, which could be controlled with antihistamines. Vaccinations should therefore only be administered in a clinic where immediate treatment of severe allergic reactions is possible. Thus, after vaccinations, patients will be closely monitored during one hour after injection to provide means for immediate treatment of allergic reactions. In addition to the standard of care, the patients participating in the trial will receive three vaccinations with Hespecta for the induction of a strong and broad CTL response against HPV16 E6. Study patients will not be paid for their participation however any study-related travel expenses will be reimbursed.

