### 7.4.2. Vaccination 1 (Week 0)

Prior to vaccination:

- Inspect the intended vaccination site for any skin abnormalities. Only continue vaccination when the skin is intact
- Vital signs (heart rate, respiratory rate, body temperature and blood pressure)

Vaccination:

- Inject the vaccine i.d. in either one of the thighs or of the upper arms. Injection may only be done by qualified study staff under medical supervision.

1 hour after each vaccination:

- Vital signs (heart rate, respiratory rate, body temperature and blood pressure)
- Examination of the inoculation site
- Registration of AE (with special emphasis on the vaccination sites)

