### 7.4.3. Vaccination 2 (Week 3 ± 2days) and vaccination 3 (Week 6 ± 2days)

Before second and third vaccination:

NL48274.000.14

Phase I Study: Hespecta vaccination in HPV+ lesions

- Inspect the intended vaccination site for any skin abnormalities
- Standard physical examination
- Vital signs (heart rate, respiratory rate, body temperature and blood pressure)
- Collection of blood samples for safety parameters (Chemistry and hematology, see paragraph 7.8)
- Collection of blood samples for immunology (only before third vaccination)
- Documentation of concomitant medications
- Urine pregnancy testing (female of child-bearing potential only)
- Documentation of AE (with special emphasis on the vaccination site)
- Inspection and measure of previous inoculation sites

Vaccination:

- Inject the vaccine i.d., in either one of the thighs or of the upper arms. Injection may only be done by qualified study staff under medical supervision.

1 hour after each vaccination:

- Vital signs (heart rate, respiratory rate, body temperature and blood pressure)
- Examination of the inoculation site, and also of previous inoculation sites
- Registration of AE (with special emphasis on the vaccination sites)

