#### **7.4.5. Follow up for immunological and safety assessments (Week 17 ± 1 week), (Week 26 ± 1 week)**

- Patients will return to the clinic 11 weeks ± 1 week) and 20 weeks ± 1 week after the last vaccination for assessment of the immunological and safety parameters. These visits are combined with regular follow up visits. If during the first follow-up visit (week 9) no abnormalities are found, it is to be expected that also at the second monitoring visit no abnormalities are found. Therefore if no abnormalities are found during the first monitoring

visit, the second monitoring visit may take place by telephone (week 17). Standard physical examination

- Documentation of concomitant medications
- Collection of blood samples for safety parameters (Chemistry and hematology, see paragraph 7.8), only week 26 ± 1 week
- Collection of blood samples for immunology, only week 26 ± 1 week
- Documentation of AE (with special emphasis on the vaccination sites)
- Inspection and measure of previous inoculation sites

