### 10.3. Benefits and risks assessment, group relatedness

Potential risks with the current trial are mainly linked to the toxicity related to the treatment compounds utilized, the Hespsecta. Although the rabbit toxicity testing of Hespsecta (see IMPD brochure) did not show any severe side effects, we expect from previous results with HPV16-SLP, that the most important AEs of Hespsecta may consist of fever, chills, nausea, malaise, fatigue and local reactions at the vaccination site including pain, redness, swelling and itching. Generally the AEs after vaccination with HPV16-SLP did not exceed grade 2 according to the CTCAE criteria. Almost all patients, with advanced CxCa as well as patients with CIN or VIN, vaccinated with HPV16-SLP formulated in Montanide ISA51 experienced local injection site reactions (grade 2). After vaccination, ulceration/abscess formation occasionally occurred, estimated to be in between 1 and 5% of vaccinations and in the order of 5.5% of patients, due to the use of this Montanide as adjuvant. The current vaccine is administered without Montanide, and therefore, it is expected that these local reaction will be less severe.

Allergic reactions have occurred in a few patients after HPV16-SLP vaccinations, controlled with antihistamines. Vaccinations should therefore only be administered in a clinic where immediate treatment of severe allergic reactions is possible. Thus, after vaccinations, patients will be closely monitored during one hour after injection to provide means for immediate treatment of allergic reactions if that would be necessary (precautions include availability of staff well-trained in resuscitation, intravenous access for administration of fluids, antihistamines and corticosteroids, and epinephrine for intramuscular injection).

All persons participating in this trial will receive the standard treatment they would have been offered outside of this clinical trial, allowing them to benefit from the normal standard of care as any patient with an HPV16+ tumor or premalignant lesion in the specified settings. At least on month following the standard of care, the patients participating in this trial will receive three vaccinations with Hespsecta for

NL48274.000.14

Phase I Study: Hespsecta vaccination in HPV+ lesions

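### Adverse events are collected unsolicited, with no scheduled contact from 1 hour to about 3 weeks after each injection, so transient expected reactions are liable to be under-recorded

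*Protocol*

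**What the plan says.** **Endpoint.** Section 7.2 states: "Safety will be determined by the incidence rate at each dose level based on the following safety parameters". The parameters are adverse events and serious adverse events, laboratory values, physical examination, vital signs and performance status, under CTCAE version 4.0.

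**Collection rule.** Section 8.2.1 states: "All AEs reported spontaneously by the subject or observed by the investigator or his staff will be recorded".

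**Expected reactions.** According to section 10.3, "the most important AEs of Hespsecta may consist of fever, chills, nausea, malaise, fatigue and local reactions at the vaccination site"; it goes on to list pain, redness, swelling and itching at the site.

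**After each injection.** The synopsis says that "patients will be closely monitored during one hour after injection to provide means for immediate treatment of allergic reactions". The steps at one hour (7.4.2, repeated in 7.4.3) are vital signs, examination of the site and "Registration of AE (with special emphasis on the vaccination sites").

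**Next contact.** After injections 1 and 2 this is the next vaccination visit, headed "Vaccination 2 (Week 3 ± 2days) and vaccination 3 (Week 6 ± 2days"). After injection 3 it is the week 9 visit, 3 weeks ± 2 days later (7.4.4). At these visits adverse events are documented with emphasis on the vaccination site, earlier sites are inspected and measured, the patient is examined, blood is taken and concomitant medication is recorded.

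**Week 17.** Section 7.4.5 lists inspection and measurement of earlier sites under the week 17 and week 26 visits, but also says that, where week 9 showed no abnormalities, "the second monitoring visit may take place by telephone (week 17"). In the schedule of events (7.3.2), footnote 7 drops only the physical examination and vital signs when the visit is by telephone.

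**The concern.** Most of the reactions named in section 10.3 are symptoms, or signs that can resolve within days. Staff cannot see them at a visit three weeks later, and the rule in 8.2.1 otherwise relies on the patient volunteering them. The emphasis written into the visits is on the vaccination site, not on systemic symptoms. A fever or a spell of chills that came and went in the first days is then recorded only from recall, and its CTCAE grade rests on memory.

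Per-dose incidence is the safety endpoint, and the IDMC charter (Appendix 2, 14.2.2) says that escalation is decided on accumulated safety data alone. This is the first use of the vaccine in humans (section 12.1), so its reactogenicity profile is one of the main things the trial can deliver.

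**Working it through.** **1. Size of the study.** 4 dose groups × 6 patients = 24, as stated in the protocol. With three injections each there are 24 × 3 = 72 post-injection intervals.

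**2. Gap without scheduled contact.** Last observation: 1 hour. Next scheduled contact: nominally 21 days.
- Nominal gap: 21 days minus 1 hour.
- With ± 2 days on the later visit: 19 to 23 days.
- Between injections 2 and 3, if the two windows move in opposite directions: 21 ± 4 = 17 to 25 days.

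The one observed hour is 1/(21 × 24) = 1/504, about 0.2% of the interval. This measures clinic presence only; adverse events documented at the next visit can still refer back to the whole interval.

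**3. What the three-weekly visit can still find.**

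| Event | How it is found as written |
|---|---|
| Site lesion that persists | Inspected and measured by staff |
| Laboratory change still present | Blood sample |
| Serious event | Likely known through care or the patient |
| Treated fever or pain | Possibly through the concomitant medication record |
| Resolved redness or swelling; site pain, itching | Patient report only |
| Chills, fever, fatigue, malaise or nausea that has passed | Patient report only |

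**4. Direction.** If *p* is the true proportion of patients with a reaction and *C* the probability that an affected patient is recorded, the expected recorded proportion is *p* × *C*. It lies below *p* for any *C* < 1.

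**5. Why the size cannot be fixed.** The protocol gives no value for *C*. It also depends on how often a patient reacts. If each reaction is captured with probability *c*, independently, over *k* injections, then *C* = 1 − (1 − *c*)^*k*. Taking *c* = 0.5 to 0.8 purely as an assumption:
- *k* = 1: *C* = 0.50 to 0.80.
- *k* = 3: *C* = 1 − 0.5³ to 1 − 0.2³ = 0.875 to 0.992.

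The loss in patient-level incidence thus runs from half to under 1% within one assumed range. Even where a patient is counted, the worst grade may be missed.

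**6. Sensitivity of the stopping rule (illustration only).** Section 3 ends escalation when two or more patients have related grade 3 or 4 toxicity. With an assumed true rate of 0.20 in 6 patients, P(at least 2 recorded) is the binomial tail at 0.20 × *C*:
- *C* = 1: 1 − 0.8⁶ − 6(0.2)(0.8⁵) = 0.345.
- *C* = 0.75 (rate 0.15): 0.224.
- *C* = 0.5 (rate 0.10): 0.114.

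Both inputs are assumed. Nothing in the protocol shows that grade 3 or 4 events would be missed at such rates.

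**7. Week 17.** A site cannot be inspected and measured by telephone. Footnote 7 does not release that item, and the schedule table has no site-inspection row to which it could attach. With a telephone visit, sites go uninspected from week 9 to week 26, which is 26 − 9 = 17 weeks.

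**The case against.** The strongest reply is that section 8.2.1 does not rest on volunteered reports alone. It includes what staff observe, and the visits put that into practice: an adverse-event entry by CTCAE at every vaccination and follow-up visit, measurement of earlier sites, laboratory tests, and a concomitant medication record that can reveal paracetamol or antihistamine use. Nothing says that staff ask no questions, patients may call at any time, and a checklist could sit in the case report form, which is not shown.

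Much of this stands. It rules out saying that there is no contact at all, or that events are never elicited. It does not close the gap: no scheduled contact falls within the three weeks, no solicited instrument for systemic symptoms is described, and a checklist in the case report form would go beyond the rule as written, so 8.2.1 would still need amending.

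The gap is also the same at every dose, so no distortion of the comparison between doses is shown. That is correct, but both the reported incidence and the stopping count are absolute figures.

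On week 17, the telephone option is conditional on a clean week 9 visit, and adverse events are still collected by telephone. The mismatch is therefore a limited one of wording.

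**Conclusion.** The point holds as a likely downward bias in the recorded incidence and grade of transient reactions, mainly mild or moderate systemic symptoms and site reactions that resolve. It rests on two things the text shows, unsolicited collection and a gap of about three weeks, and on the assumption that some patients forget or do not mention a resolved reaction. It is weaker for persistent lesions, serious events and laboratory changes.

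Three stronger readings are tempting and not supported:
- A reader might infer that events **are** under-counted and under-graded at every dose level by a definite amount. With no onset time, duration or capture rate in the protocol, no recorded-versus-true figure can be given.
- A reader might infer that the stopping rule is compromised. It counts related grade 3 or 4 toxicity, and no loss of such events is shown.
- A reader might infer that the expected improvement over the Montanide formulation would appear partly as an artefact. The protocol does not say how the earlier trials collected adverse events, and section 9 plans no comparison with them.

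The week 17 mismatch is real, minor and separate.

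**What to change.** In section 8.2.1, add solicited collection for the reactions already listed in 10.3:
- a fixed checklist asked at every existing visit or telephone contact;
- a short paper diary for the days after each injection, covering temperature, the listed systemic symptoms, and the presence and size of site reactions, reviewed with the patient and CTCAE-graded at the next visit.

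The sponsor should state how many days the diary covers. Unsolicited events continue to be recorded as now, and the tables should keep solicited and unsolicited events apart.

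Separately, reconcile the site-inspection item in 7.4.5 with the telephone option at week 17 and with footnote 7 of the schedule, so that the three texts agree.

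Cost: one protocol paragraph, one checklist page, one paper diary and one wording edit, with no extra visit or staff. The downside is a small burden on patients and higher reported rates of mild reactions, which the report should explain.
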